15. APPENDICES

Appendix A: Schedule of Assessments – Cohort 1- Regorafenib then SIR-Spheres then Regorafenib

Procedures	Screening	Cohort 1 –Regorafenib then SIR-Spheres then Regorafenib									End of Treatment Visit ^l	Follow-Up				
		Regorafenib				SIR-Spheres		Regorafenib								
		Cycle 1				Cycle 2		Cycle 3 and Beyond								
		Days				Days		Days								
		Baseline ^b	1 ^b	8	15	22 ^q	1	8	1	8	15					
TESTS & OBSERVATIONS																
Informed Consent ^a	X ^a															
Medical history	X	X														
Physical examination, vital signs, height, weight ^c	X	X	X	X	X			X			X	X				
Blood Pressure	X	X	X	X	X	X	X	X			X	X				
ECOG Performance Status	X	X	X	X				X			X	X				
Adverse event evaluation			X	X	X			X	X		X	X				
Concomitant medication review	X	X	X	X				X			X	X				
Survival Status													X			
LABORATORY TESTS																
CBC, including differential and platelets ^d	X	X	X	X	X			X			X	X				
CMP ^e	X	X	X	X		X		X ^f			X	X				
PT/PTT/INR ^g	X	X	X	X				X		X	X	X				
Serum or urine pregnancy test ⁱ	X	X														
Biomarker blood sample collection					X ^h		X ^h	X ^h (day 30)								

CONFIDENTIAL

STUDY DEVICE: SIR-Spheres®

DATE OF ORIGINAL PROTOCOL: 16 December 2013

Date of Amendment #1: 15 April 2014

SCRI INNOVATIONS STUDY NUMBER: GI 189

Version 2.0

Appendix A: Schedule of Assessments – Cohort 1- Regorafenib then SIR-Spheres then Regorafenib

Procedures	Screening	Cohort 1 –Regorafenib then SIR-Spheres then Regorafenib									End of Treatment Visit ^l	Follow-Up				
		Regorafenib				SIR-Spheres		Regorafenib				Disease-Free Survival ^m	Survival ⁿ			
		Cycle 1				Cycle 2		Cycle 3 and Beyond								
		Days				Days		Days								
		Baseline ^b	1 ^b	8	15	22 ^q	1	8	1	8	15					
DISEASE ASSESSMENT																
CT scan of the chest, abdomen, pelvis ^{j,k}	X									X ^j	X ^j	X ^j				
Tumor marker (CEA)	X	X			X			X			X					
Hepatic angiogram					X ^o											
^{99m} Tc MAA lung shunt scan ^o					X ^o											
TREATMENT																
Regorafenib PO (Days 1-21) ^p		Days 1-21						Days 1-21								
SIR-Spheres						X										

STUDY DEVICE: SIR-Spheres[®]
 DATE OF ORIGINAL PROTOCOL: 16 December 2013
 Date of Amendment #1: 15 April 2014

CONFIDENTIAL
 SCR INNOVATIONS STUDY NUMBER: GI 189

Version 2.0

Appendix A: Cohort 1 Schedule of Assessments (continued)

- a. Informed Consent must be obtained ≤ 28 days prior to the initiation of study treatment.
- b. The Screening physical examination, update of medical history, ECOG performance status, CBC, CMP, and PT/PTT/INR, and concomitant medication review should be done ≤ 21 days prior to initiation of treatment. However, if these initial examinations are obtained within 72 hours of Cycle 1 Day 1 they do not have to be repeated on Cycle 1 Day 1. Scans to document measurable or evaluable disease (i.e., tumor measurement) and tumor marker (CEA) should be performed ≤ 28 days prior to initiation of treatment.
- c. Physical examinations will include measurements of height (Screening visit only), weight and vital signs (resting heart rate, respiratory rate, oral temperature). Blood pressure should be monitored weekly for the first 6 weeks of regorafenib treatment and then every cycle, or more frequently, if clinically indicated.
- d. Hematology parameters include the following laboratory tests: complete blood count including WBC with 3-part differential (total neutrophil count including bands, lymphocytes, monocytes) hemoglobin, hematocrit and platelets.
- e. CMP must include glucose, BUN, creatinine, sodium, potassium, chloride, calcium, CO₂, ALP, AST, ALT, total bilirubin, total protein, and albumin plus LDH, phosphorus.
- f. If liver function toxicities are present after a 2 week rest, then patients may be rechecked weekly for 2 additional weeks. Reinitiation of regorafenib must be delayed until appropriate resolution of liver function toxicities.
- g. PT/PTT/INR will be monitored in patients receiving Coumadin on Days 1, 8 (Cycle 1 only) and 15 of each treatment cycle.
- h. Biomarker samples (see Section 5.4) will be collected from all patients prior to the hepatic angiogram and ^{99m}Tc MAA lung shunt scan, which will be obtained 7-4 days prior to SIR-Spheres treatment (see Section 7.2) and on Day 8 after SIR-Spheres treatment and Day 30 (pre-dose) after SIR-Spheres treatment.
- i. Serum or urine pregnancy tests are to be conducted in women of childbearing potential within 72 hours of C1D1.
- j. CT scan of the chest, abdomen and pelvis will be obtained at baseline ≤ 28 days prior to the initiation of treatment. Assessments required the same day of SIR-Spheres administration can be obtained ≤ 7 days prior to SIR-Spheres treatment. Patients will be restaged on Week 6 and Week 12 after SIR-Spheres treatment according to RECIST v1.1. All assessments should be performed within 7 days of the schedule day of assessment. Patients with stable disease or better may continue treatment with regorafenib. CEA tumor markers must be assessed on Day 1 of each cycle and at the End of Treatment visit.
- k. Patients determined to have stable disease or better at the Week 12 restaging continuing treatment will begin 28-day treatment cycles (21 days oral regorafenib followed by one week rest). Patients will then be re-assessed according to RECIST v1.1 criteria every 8 weeks.
- l. All patients will undergo the End of Treatment visit assessments listed within 30 days after treatment ends due to completion of the planned study treatment period, or once a patient is discontinued due to unacceptable toxicity or decision to discontinue treatment by the patient or the study physician. If treatment is discontinued because of toxicity or any other reason(s) at a treatment visit and no study treatment is administered, that visit may fulfill the End of Treatment visit. After withdrawal from or completion of protocol treatment, patients must be followed for adverse events for 30 calendar days after the last dose of study drug.
- m. Patients will be followed every 3 months (± 1 month) for up to a maximum of 6 months after the last patient has enrolled on study for toxicity and disease progression.
- n. After disease progression is documented, patients will be followed every 3 months (± 1 month) for survival (e.g., date and cause of death) for up to a maximum of 6 months after the last patient has enrolled on study or death whichever comes first. Patients may be contacted during outpatient visits or by telephone.
- o. Patients will be assessed 7-4 days prior to SIR-Spheres treatment to determine the suitability for SIR-Spheres (see Section 7.2).
- p. Patients will self-administer regorafenib during Days 1-21.
- q. The Cycle 1 Day 22 physical examination, ECOG performance status, CBC, CMP, and PT/PTT/INR, tumor marker (CEA), adverse event evaluation, and concomitant medication review to be completed ≤ 7 days prior to SIR-Spheres radiation treatment.

STUDY DEVICE: SIR-Spheres®

DATE OF ORIGINAL PROTOCOL: 16 December 2013

Date of Amendment #1: 15 April 2014

CONFIDENTIAL

SCRI INNOVATIONS STUDY NUMBER: GI 189

Version 2.0

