5. STUDY DESIGN

This is an open-label study comparing the safety of two treatment cohorts in which radioembolization will be administered using the device SIR-Spheres in combination with regorafenib to patients with mCRC with liver metastases. The two treatment cohorts will be evaluated for safety, ORR, PFS, and OS. Twenty-five patients will be treated in each cohort. The first cohort will complete enrollment before the second cohort opens. There will be no randomization or blinding.

A safety review for toxicity by the Medical Monitor will occur after the first 10 patients have been enrolled in each cohort and treated with one cycle of regorafenib and SIR-spheres (combination therapy) to assess the frequency of \geq Grade 3 adverse events and all SAEs. Accrual will not be halted while the analysis is being conducted.

Stopping Rules Due to Toxicities of Combination Therapy

Stopping rules due to toxicities assessed as related to combination therapy by the Medical Monitor will be defined as follows:

CONFIDENTIAL

STUDY DEVICE: SIR-Spheres®

SCRI INNOVATIONS STUDY NUMBER: GI 189

DATE OF ORIGINAL PROTOCOL: 16 December 2013

Date of Amendment #1: 15 April 2014

Version 2.0

- A patient death considered to be caused by AEs of combination therapy
- A patient with Grade 4 AST, ALT, or irreversible hepatic failure assessed as related to combination therapy;
- More than 2 patients that develop Grade 3 AST, ALT, or total bilirubin assessed as related to combination therapy;
- More than 2 patients develop Grade 3 bleeding in the lung, stomach, small intestine, or liver assessed as related to combination therapy.

If the early stopping rules are met or safety signals emerge from the group of the first 10 patients treated with combination therapy in each cohort, patient recruitment will discontinue and the study will be reassessed. Any outcome of these safety reviews will be communicated in a timely manner to the participating investigators so that they may notify their IRBs.

Blood samples will be collected from all patients prior to the hepatic angiogram and ^{99m}Tc MAA lung shunt scan, on Day 8 after SIR-Spheres treatment, and Day 30 (pre-dose) after SIR-Spheres treatment (see Section 5.1). Expressions of cytokines and proteins will be measured to explore potential biomarkers that may correlate with clinical outcome. The study schema is presented in Figure 1.

CONFIDENTIAL

STUDY DEVICE: SIR-Spheres®

SCRI INNOVATIONS STUDY NUMBER: GI 189

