- Biomarker blood sample collection prior to the hepatic angiogram and 99m Tc MAA lung shunt scan
- CEA tumor marker

The following tests will be obtained 7-4 days prior to SIR-Spheres treatment:

- Hepatic angiogram
- 99m Tc MAA lung shunt scan

7.3.5 Cycle 2, Day 1

SIR-Spheres may not be administered until the patient's hematologic, liver and renal function assessments performed per Section 7.3.4 have been re-confirmed as eligible according to Section 3.1 by the Investigator.

- SIR-Spheres treatment
- BP

CONFIDENTIAL

STUDY DEVICE: SIR-Spheres®

SCRI INNOVATIONS STUDY NUMBER: GI 189

DATE OF ORIGINAL PROTOCOL: 16 December 2013

Date of Amendment #1: 15 April 2014

Version 2.0

7.3.6 Cycle 2, Day 8

- BP
- AE assessment
- CMP
- Biomarker blood sample collection (following SIR-Spheres treatment)

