7.3.7 Cycle 3 and Beyond, Day 1 (± 72 hours)

Regorafenib may not start until the patient's hematologic, liver and renal functions have been reconfirmed as eligible according to the Section 3.1 by the Investigator. Therefore, the regorafenib cycle starts on the day that treatment begins. If liver function toxicities are present, patient may be rechecked weekly for 2 additional weeks. Those patients with persistent liver function toxicities after this time will come off study, but will be followed until resolution.

- Physical examination, weight, and vital signs
- BP
- ECOG PS
- AE assessment
- Concomitant medication review
- CBC
- CMP
- PT/PTT/INR (for patients receiving Coumadin therapy)
- Biomarker blood sample collection (Day 30 (pre-dose) following SIR-Spheres treatment)
- CEA tumor marker

7.3.8 Cycle 3 and Beyond, Day 15

- PT/PTT/INR (for patients receiving Coumadin therapy)

7.4 Study Treatment Assessments – COHORT 2

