7.4.4 Cycle 2, Day 1 (± 72 hours)

Regorafenib may not start until the patient's hematologic, liver and renal functions have been re-confirmed as eligible according to Section 3.1 by the Investigator. Therefore, the regorafenib cycle starts on the day that treatment begins. If liver function toxicities are present, patient may be rechecked weekly for 2 additional weeks. Those patients with persistent liver function toxicities after this time will come off study, but will be followed until resolution.

CONFIDENTIAL

STUDY DEVICE: SIR-Spheres®

SCRI INNOVATIONS STUDY NUMBER: GI 189

DATE OF ORIGINAL PROTOCOL: 16 December 2013

Date of Amendment #1: 15 April 2014

Version 2.0

- Physical examination, weight, and vital signs
- BP
- ECOG PS
- AE assessment
- Concomitant medication review
- CBC
- CMP
- PT/PTT/INR (for patients receiving Coumadin therapy)
- CEA tumor marker
- Biomarker blood sample collection (Day 30 following SIR-Spheres treatment only)

7.4.5 Cycle 2, Day 8 and 15

- Physical examination, weight, and vital signs
- BP
- ECOG PS
- AE assessment
- Concomitant medication review
- CBC
- CMP
- PT/PTT/INR (for patients receiving Coumadin therapy)

7.4.6 Cycle 2, Day 22

- BP

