- j. CT scan of the chest, abdomen and pelvis will be obtained at baseline ≤ 28 days prior to the initiation of treatment. Assessments required the same day of SIR-Spheres administration can be obtained ≤ 7 days prior to SIR-Spheres treatment. Patients will be restaged on Week 6 and Week 12 after SIR-Spheres treatment according to RECIST v1.1. All assessments should be performed within 7 days of the schedule day of assessment. Patients with stable disease or better may continue treatment with regorafenib. CEA tumor markers must be assessed on Day 1 of each cycle and at the End of Treatment visit.
- k. Patients determined to have stable disease or better at the Week 12 restaging continuing treatment will begin 28-day treatment cycles (21 days oral regorafenib followed by one week rest). Patients will be re-assessed according to RECIST v1.1 criteria every 8 weeks.
- l. All patients will undergo the End of Treatment visit assessments listed within 30 days after treatment ends due to completion of the planned study treatment period, or once a patient is discontinued due to unacceptable toxicity or decision to discontinue treatment by the patient or the study physician. If treatment is discontinued because of toxicity or any other reason(s) at a treatment visit and no study treatment is administered, that visit may fulfill the End of Treatment visit. After withdrawal from or completion of protocol treatment, patients must be followed for adverse events for 30 calendar days after the last dose of study drug.
- m. Patients will be followed every 3 months (± 1 month) for up to a maximum of 6 months after the last patient has enrolled on study for toxicity and disease progression.
- n. After disease progression is documented, patients will be followed every 3 months (± 1 month) for survival (e.g., date and cause of death) for up to a maximum of 6 months after the last patient has enrolled on study or death whichever comes first. Patients may be assessed during outpatient visits or contacted by telephone.
- o. Patients will self-administer regorafenib during Days 1-21.
- p. Blood pressure is required Cycle 3 Day 8. Cycle 4 and beyond, blood pressure will be required Day 1 only.

CONFIDENTIAL

SCRI INNOVATIONS STUDY NUMBER: GI 189

STUDY DEVICE: SIR-Spheres®

DATE OF ORIGINAL PROTOCOL: 16 December 2013

Date of Amendment #1: 15 April 2014

Version 2.0

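### In the first regorafenib cycle after SIR-Spheres, Cohort 1 has no scheduled BP, AE, CBC or CMP check after Day 1, while Cohort 2 has all four on Days 8 and 15, so by-cohort laboratory and BP results for the combination phase rest on unequal ascertainment

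*Protocol*

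**What the plan says.** Protocol Section 5 states: "This is an open-label study comparing the safety of two treatment cohorts". The cohorts enrol one after the other, without randomisation.

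Cohort 1 takes one cycle of regorafenib, has SIR-Spheres on Cycle 2 Day 1, and restarts regorafenib at Cycle 3 Day 1. Section 7.3.7 lists BP, AE, CBC and CMP for that Day 1. No section covers Cycle 3 Day 8. The section headed "7.3.8 Cycle 3 and Beyond, Day 15" lists only clotting tests for patients on Coumadin.

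Cohort 2 has SIR-Spheres on Cycle 1 Day 1 and starts regorafenib at Cycle 2 Day 1. The section headed "7.4.5 Cycle 2, Day 8 and 15" lists examination, BP, ECOG, AE, CBC and CMP at both visits. The section headed "7.4.6 Cycle 2, Day 22" adds a BP reading. Appendix B adds another: "Blood pressure is required Cycle 3 Day 8".

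Footnote c of both appendices gives the general BP rule: "Blood pressure should be monitored weekly for the first 6 weeks of regorafenib treatment", and every cycle after that.

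Protocol 10.4.4 summarises AEs by cohort and laboratory results for the Safety Population. The SAP's safety section summarises laboratory data by CTCAE grade. Neither document allows for a difference in how often the cohorts are tested.

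**The concern.** An asymptomatic rise in transaminases or bilirubin, a fall in counts or a rise in BP is found only if someone measures it. If one cohort is measured twice in a cycle and the other not at all, the first will tend to show more such findings and higher worst grades even when the true rates are equal.

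The gap falls where the combination is under test. Protocol 8.1.3 places radioembolization-induced liver disease at about 4-8 weeks after treatment, with raised bilirubin as its usual marker. Under Protocol 11.3.3 a laboratory abnormality becomes an AE when, for example, it leads to a dose change. Unequal testing can therefore also reach the AE-by-grade tables, including SAP Table 8.

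**Working it through.** The plan gives no figure to reproduce, so the check is a count of scheduled visits.

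**Time axis.** SIR-Spheres is Day 1. With the two-week rest, regorafenib starts or restarts on Day 15. Days 8, 15 and 22 of that cycle are study Days 22, 29 and 36, and the next cycle starts on Day 43.

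**Scheduled checks (Sections 7.3.5-7.3.7 and 7.4.2-7.4.7), Cohort 1 versus Cohort 2**

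| Check | Cohort 1 days | Cohort 2 days | Days 16-42 | Days 2-42 |
|---|---|---|---|---|
| BP | 1, 8, 15, 43 | 15, 22, 29, 36, 43 | 0 vs 3 | 2 vs 4 |
| AE | 8, 15, 43 | 8, 15, 22, 29, 43 | 0 vs 2 | 2 vs 4 |
| CBC | 15, 43 | 15, 22, 29, 43 | 0 vs 2 | 1 vs 3 |
| CMP | 8, 15, 43 | 8, 15, 22, 29, 43 | 0 vs 2 | 2 vs 4 |

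For AE, CBC and CMP, the longest gap in this cycle is 43 − 15 = 28 days in Cohort 1 and 43 − 29 = 14 days in Cohort 2. In the 4-8 week window (Days 29-57), CMPs number 1 (Day 43) versus 2 (Days 29 and 43).

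**What the gap could do (assumed inputs).** Take an asymptomatic abnormality with onset day d uniform over Days 16-42 (27 days), lasting L days. A visit on day v detects it if d ≤ v ≤ d + L − 1.

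- L = 7, Cohort 1: only Day 43 can detect it, for d = 37-42, so 6/27 = 22%.
- L = 7, Cohort 2: Day 22 (7 onset days), Day 29 (7) and Day 43 (6), so 20/27 = 74%.
- L = 14: Cohort 1 needs d = 30-42, so 13/27 = 48%; Cohort 2 27/27 = 100%.
- L = 21: Cohort 1 needs d = 23-42, so 20/27 = 74%; Cohort 2 100%.
- L = 28: 100% in both.

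The difference therefore matters for short-lived abnormalities and disappears for those lasting four weeks.

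**Counting from first treatment.** Before the second regorafenib cycle after SIR-Spheres, Cohort 1 has 5 post-baseline CMPs (Cycle 1 Days 8, 15, 22; Cycle 2 Day 8; Cycle 3 Day 1). Cohort 2 has 4 (Cycle 1 Day 8; Cycle 2 Days 1, 8, 15). Cohort 1's window is longer: 28 + 14 + 28 = 70 days against 14 + 28 = 42.

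**Footnote c.** In calendar weeks from the first dose, Cohort 1 has BP at Cycle 1 Days 1, 8, 15, 22 and Cycle 2 Days 1, 8. Cohort 2 has it at Cycle 2 Days 1, 8, 15, 22 and Cycle 3 Days 1, 8. Both have six.

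**A check against the PDF.** Read as text, the AE row of the Appendix A grid appears to have a mark under Cycle 3 Day 8 and none under Cycle 2 Day 8. Section 7.3.6 requires AE at Cycle 2 Day 8 and no section requires it at Cycle 3 Day 8, so a column shift is the likely explanation. If the mark is real, the AE count for Days 16-42 is 1 versus 2.

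**The case against.** The schedule has a coherent logic. Each cohort is watched closely in its own first regorafenib cycle, and after that toxicity is evaluated at the start of each cycle (Protocol 5.2). Cohort 1 does have the full panel on Days 8 and 15 of Cycle 1 (7.3.3). That stands as an explanation, but those visits precede SIR-Spheres and observe regorafenib alone. They say nothing about the combination.

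AEs are recorded continuously (11.1.5), and Table 3 triggers frequent liver tests after an abnormality. This stands for symptomatic events. It helps less with silent ones, because the Table 3 tests start only once an abnormal result has been seen.

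The SAP plans no between-cohort laboratory or BP comparison. Its only between-cohort estimate is the difference in response rates, and there is no hypothesis testing. This stands too and limits the weight of the point. Descriptive results by cohort will still be read side by side in a study described as a comparison.

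Three stronger readings are tempting and are not supported:

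- A reader might infer that Cohort 1's schedule breaks footnote c. It does so only if weeks on drug are counted. Cohort 2's schedule includes Day 22, a drug-free week, and ends at Cycle 3 Day 8, so the protocol appears to count calendar weeks, and both cohorts comply.
- A reader might infer that any excess of findings in Cohort 2 is due purely to more frequent looking. Continuous AE recording, triggered tests and sequential non-randomised enrolment rule out so simple an attribution.
- A reader might infer that all safety results are biased against Cohort 2. From first treatment, the CMP counts are 5 versus 4, over windows of different length, with no clear direction.

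**Conclusion.** The point holds for laboratory and BP results in the combination phase. In the first regorafenib cycle after SIR-Spheres, scheduled checks between Day 1 and the next cycle are 0 versus 3 for BP and 0 versus 2 for each of AE, CBC and CMP. The longest gap between CMPs is 28 versus 14 days. These within-cycle counts follow from the text of Sections 7.3 and 7.4, subject to the check of the Appendix A AE row; the study-day labels assume a two-week rest.

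The detection figures (22% versus 74% for 7-day abnormalities, 48% versus 100% for 14-day ones) also assume uniform onset over Days 16-42, which is exactly Cohort 1's unmonitored interval. They illustrate the possible size and are not estimates. The liver stopping rule draws on the same tests, but any effect on it cannot be sized from the documents.

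The point is worth acting on in the SAP. It does not invalidate the within-cohort safety results.

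**What to change.** In the SAP, wherever laboratory or BP results after SIR-Spheres are shown side by side by cohort, add a summary restricted to visits that both cohorts share:

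- CMP: Day 8 after SIR-Spheres, Day 1 of the first regorafenib cycle after SIR-Spheres, and Day 1 of the next cycle.
- BP and CBC: the two cycle Day 1 visits only, because Section 7.4.3 lists neither at Day 8 after SIR-Spheres.

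Key the summary to the visit, not to fixed Days 15 and 43, since regorafenib may start 2-4 weeks after SIR-Spheres and the cycle Day 1 visits have a 72-hour window. Give the number of patients with a value at each visit. Present full-schedule results within cohort, with a note that Cohort 2 had more scheduled checks in this cycle.

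The cost is SAP wording and some programming, using data already due to be collected. The shared-visit summary has fewer data points and cannot recover short-lived abnormalities that fell between visits.

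Separately, the sponsor should reconcile Sections 7.3.7-7.3.8 with 7.4.5, or state that the difference is intended. Which monitoring schedule applies is the sponsor's decision. Footnote c needs no change on this account.

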Appendix B: Schedule of Assessments - Cohort 2-SIR-Spheres then Regorafenib

Procedures	Screening	Cohort 2 – SIR-Spheres then Regorafenib									End of Treatment Visit ^l	Follow-Up				
		SIR-Spheres		Regorafenib								Disease-Free Survival ^m	Survival ⁿ			
		Cycle 1		Cycle 2				Cycle 3 and Beyond								
		Days		Days				Days								
		Baseline ^b	1	8	1	8	15	22	1	8	15					
TESTS & OBSERVATIONS																
Informed Consent ^a		X ^a														
Medical history		X														
Physical examination, vital signs, height, weight ^c		X			X	X	X		X		X	X				
Blood Pressure		X			X	X	X	X	X	X ^p	X	X				
ECOG Performance Status		X			X	X	X		X		X	X				
Adverse event evaluation			X	X	X	X		X		X	X					
Concomitant medication review		X			X	X	X		X		X	X				
Survival Status													X			
LABORATORY TESTS																
CBC, including differential and platelets ^d		X			X	X	X		X		X	X				
CMP ^e		X		X	X ^f	X	X		X		X	X				
PT/PTT/INR ^g		X			X	X	X		X		X	X				
Serum or urine pregnancy test		X ⁱ														
Biomarker blood sample collection		X ^h		X ^h	X ^h (day 30)											

STUDY DEVICE: SIR-Spheres[®]
 DATE OF ORIGINAL PROTOCOL: 16 December 2013
 Date of Amendment #1: 15 April 2014

CONFIDENTIAL
 SCRIB INNOVATIONS STUDY NUMBER: GI 189

Version 2.0

